### 8.2.5 Study Follow-up

Follow-up will be evaluated in two ways. With an 'intention-to-treat' analysis, patients will be followed for all available time after they initiate a medication, irrespective of whether they discontinue the medication or not, or whether they switch to an alternate medication or not. Follow-up begins the day after the index date and ends at first occurrence of: (a) the outcome of interest, (b) disenrollment from a health plan, or (c) end of study period.

With a 'per-protocol analysis' patients are followed for as long as they are actively taking the medication of interest during the follow-up period. Follow-up begins the day after the index date and ends at first occurrence of: (a) the outcome of interest, (b) disenrollment from the health plan, (c) discontinuation of study medication, (d) switching to the alternate medication, or (e) administrative end of study. When a gap greater than the allowable gap of 30 days is encountered, discontinuation of study medication occurs at the end of the last prescription which includes the days supply (+60 day extension). Censoring due to switching will occur for the new user cohorts in this study when the following conditions are met:

- (1) For new users of erenumab-aooe, initiation of any other medication targeting the CGRP pathway (galcanezumab-gnlm, fremanezumab-vfrm, eptinezumab-jjmr, ubrogepant, rimegepant) during the follow-up period.
- (2) For new users of other mAbs targeting the CGRP pathway, initiation of erenumab-aooe, ubrogepant, or rimegepant during the follow-up period.
- (3) For new users of the SOC migraine preventive medications (anti-epileptics), initiation of any medication targeting the CGRP pathway (erenumab-aooe, galcanezumab-gnlm, fremanezumab-vfrm, eptinezumab-jjmr, ubrogepant, rimegepant) during the follow-up period.
- (4) For new users of onabotulinumtoxinA, initiation of any medication targeting the CGRP pathway (erenumab-aooe, galcanezumab-gnlm, fremanezumab-vfrm, eptinezumab-jjmr, ubrogepant, rimegepant) during the follow-up period.

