#### 8.3.4 Validity and Reliability

We will use validated definitions where appropriate to identify the cardiovascular events that are of interest in this study (Sentinel Initiative, 2018; McCormick et al, 2015; Sherman et al, 2013; Cutrona et al, 2013; Tirschwell and Longstreth, 2012; Quan et al, 2009; Roumie et al, 2008; Tu et al, 2007; McCormick et al, 2015).

The primary algorithm, with a positive predictive value (PPV) of 86% (95% CI: 79%, 91%), to identify acute MI requires an ICD-10-CM diagnosis code of I21.xxx or I22.xxx (see Appendix C) in the principal or primary position of facility claims for hospitalization (Cutrona et al, 2013).

As with acute MI, an algorithm to identify ischemic stroke with good PPV (90% [95% CI: 77%, 97%]) also requires an ICD-10-CM diagnosis code (I63.xxx) occurring in the primary position for facility claims for hospitalization (Tirschwell and Longstreth, 2012). In contrast, the algorithms for intracerebral hemorrhage (PPV – 89% [95% CI: 75%, 99%], ICD-10-CM diagnosis code I61.xxx) and subarachnoid hemorrhage (PPV – 94% [95% CI: 83%, 99%], ICD-10-CM diagnosis code I60.xxx) require a diagnosis code for hemorrhage that can occur in any diagnosis position for an inpatient hospitalization (Tirschwell and Longstreth, 2012). All ischemic and hemorrhagic (intracerebral and subarachnoid) stroke events will be combined to identify 'any stroke' for the primary analysis; however, the cumulative incidence of ischemic and hemorrhagic stroke events will also be described separately.

Algorithms that evaluate acute MI, ischemic stroke, and hemorrhagic stroke in either the emergency room (ER) or the inpatient setting will also be considered.

There are a number of algorithms, with varying performance characteristics, to identify clinical hypertension in administrative claims data (Sherman et al, 2013; Quan et al, 2009; Tu et al, 2007) but none to evaluate drug-induced hypertension. As a result, using the hypertension codes listed in Appendix C, we will evaluate new onset hypertension with the following algorithms:

- 1. 1 IP / 1 ER / 1 OP diagnosis (any position) of hypertension
- 2. 1 IP / 1ER / 1 OP diagnosis (any position) of hypertension, with a prescription fill for an anti-hypertensive medication within 30 days after the hypertension diagnosis date.
- 3. 1 IP / 1ER / 1 OP diagnosis of hypertension (any position), and discontinuation of the study medication within 90 days after diagnosis

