- 4. 1 IP / 1 ER / 1 OP diagnosis (any position) of hypertensive crisis
- 5. 1 IP / 1 ER diagnosis of hypertension in the primary position

New onset hypertension will be the primary hypertension outcome of interest, and the cumulative incidence of this outcome will be evaluated at 1 month, at 2 months, at 3 months, at 6 months, and at 12 months. When evaluating new onset hypertension, individuals with a prior history of hypertension during the baseline period will be excluded. For individuals with baseline hypertension and anti-hypertension medication use, we will also evaluate changes in medication dosage or initiation of new anti-hypertensive medications within 90 days after initiation of the study medication.

In addition, we will evaluate the occurrence of a single diagnosis of elevated blood pressure reading, without diagnosis of hypertension (ICD-10-CM diagnosis code R03.0) occurring in any diagnosis position in the IP, ER, or OP setting.

The algorithm used to identify patients with migraine in this study has not been validated, but a similar algorithm (Kolodner et al, 2004) had high specificity and low sensitivity. Thus, it is possible that some migraine patients will be misclassified as non-migraine patients and will be excluded from this study.

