### **Descriptive Analyses**

### Estimating the Cumulative Distribution of a Right-Censored Outcome

Following the notation by Cole et al (Cole et al, 2015) and Brookhart (Brookhart, 2019), let  $T_i$  be the continuous random variable for the time from treatment initiation to acute MI

for the  $i^{th}$  patient, and let *t* represent the realization (ie, a specific value) of  $T_{i.}$  The cumulative incidence (ie, risk) of the acute MI outcome at time *t* is the complement of the Kaplan-Meier survival function,

$$R(t)=1-S(t)=\Pr(T_i < t).$$

The entire function over time is of interest, but the cumulative incidence of acute MI at times t=6 months, t=1 years, and t=2 years after the start of treatment will also be estimated.

The naïve, unadjusted cumulative incidence of the outcome, R(t), subject to rightcensoring by *C*, can be conveniently estimated with the following estimating function:

$$\widehat{Pr}(T < t) = \frac{1}{n} \sum_{i=1}^{n} \frac{\Delta_i I(T_i < t)}{Pr(\Delta_i = 1)},$$

where  $\Delta = l(T < C)$  is an indicator that the patient was uncensored. In the denominator  $Pr(\Delta_i = 1)$  implies that censoring is non-informative (ie,  $C \perp T$ ), and, so, the cumulative incidence curve that is initially estimated assumes that censoring occurs at random.

In addition to estimating the cumulative incidence, the incidence rate, overall, and by selected baseline characteristics, with 95% confidence intervals based on the Poisson distribution, will also be estimated.

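### Hypertension algorithm 3 requires stopping the drug, but per-protocol follow-up censors stopping without a diagnosis, so 1 minus Kaplan-Meier overstates its cumulative incidence

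*Protocol*

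**What the plan says.** Protocol 8.3.4 lists five algorithms for new onset hypertension. The third requires an inpatient, emergency room or outpatient hypertension diagnosis together with "discontinuation of the study medication within 90 days after diagnosis". For new onset hypertension, "the cumulative incidence of this outcome will be evaluated at 1 month, at 2 months, at 3 months, at 6 months, and at 12 months".

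Protocol 8.2.5 plans two kinds of follow-up. Intention-to-treat keeps patients under observation "irrespective of whether they discontinue the medication or not". Per-protocol follow-up stops at the first of several events, among them "c) discontinuation of study medication, (d) switching to the alternate medication, or (e) administrative end of study". The stopping date is set late: "discontinuation of study medication occurs at the end of the last prescription which includes the days supply (+60 day extension)". Section 8.3.2 ties every outcome to the follow-up defined in 8.2.5.

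Protocol 8.7.2.4, under the descriptive analyses, says that the risk at time t "is the complement of the Kaplan-Meier survival function", and that the initial curve takes censoring to be random. The formula is written out for acute MI. The data analysis part of the abstract plans the same unadjusted cumulative incidence for hypertension. Section 8.7.2.2 discusses competing risk for death only. Nothing makes an exception for algorithm 3.

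**The concern.** In the per-protocol analysis, discontinuation plays two roles for algorithm 3. After a diagnosis it completes the outcome. Without one it ends follow-up as a censoring event.

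Kaplan-Meier treats a censored patient as someone who would later have had the event at the same rate as those still observed. That cannot be true of a patient who has already stopped undiagnosed, because no later diagnosis in that treatment episode can be followed by stopping the drug. The patient's probability is nevertheless passed on to the continuers, and the reported risk comes out too high.

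Section 8.3.4 says that no claims algorithm exists for drug-induced hypertension and offers these five instead. Algorithm 3 is the only one that requires the drug to be stopped, so readers are likely to take it as the closest to a drug-attributed signal. New onset hypertension is in the labelled warnings for erenumab-aooe (6.2).

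**Working it through.** **Nothing to reproduce.** The protocol states no algorithm 3 risk and no discontinuation rate. The check compares what the planned estimator would report with the true cumulative incidence, under stated assumptions.

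**Inputs**
- Hypertension diagnosis rate λ: 0.356 per person-year, from 3.56 per 10 person-years in 6.3. The new-onset rate may be lower because baseline hypertension is excluded, so 0.10 is also used (assumption).
- 12-month persistence: 70%, 50%, 30% (assumption). Stopping rate before diagnosis μ = −ln(persistence).
- Stopping rate after diagnosis ν: 1 or 3 times μ (assumption).
- Window of 90 days, taken as 0.25 year. Times are exponential.
- Event dated at diagnosis or at discontinuation. The protocol does not say which, so both were run.

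**Formulas, event dated at diagnosis**
- Share of diagnosed patients who stop inside the window: q = 1 − exp(−0.25ν).
- True cumulative incidence at 1 year: q × λ/(λ+μ) × [1 − exp(−(λ+μ))].
- Planned estimate: 1 − exp(−∫ h(t) dt) over one year, with h(t) = λ q exp(−(λ+μ)t) / Y(t). Y(t) is the fraction still on drug and event-free, including patients whose diagnosis did not qualify.

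**Worked case: λ = 0.356, persistence 70%, ν = μ.** μ = 0.3567 and q = 1 − exp(−0.0892) = 0.0853. True incidence = 0.0853 × 0.356/0.7127 × (1 − exp(−0.7127)) = 0.0853 × 0.4995 × 0.5097 = 2.17%. The planned estimate is 2.53%.

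**Results at 12 months (λ = 0.356, ν = μ, event dated at diagnosis; simulation of 1,000,000 patients per scenario)**

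| Persistence | 1 − KM | True incidence | Excess, points | Ratio | Ratio, all scenarios |
|---|---|---|---|---|---|
| 70% | 2.53% | 2.17% | 0.36 | 1.17 | 1.17–1.21 |
| 50% | 4.69% | 3.52% | 1.17 | 1.33 | 1.33–1.44 |
| 30% | 7.55% | 4.68% | 2.87 | 1.61 | 1.61–1.83 |

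The last column covers both values of λ, both stopping multiples and both event dates. Numerical integration of the formulas agrees with these three rows to within 0.01 point. When discontinuation does not censor, as under intention-to-treat, the ratio is 1.00.

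**Effect on cohort contrasts.** In this model, two cohorts with the same λ and persistence of 70% and 30% have true risks of 2.17% and 4.68% (ratio 4.68/2.17 = 2.16). They would be reported as 2.53% and 7.55% (7.55/2.53 = 2.98), so the difference is magnified.

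A second model instead fixes the qualifying share at 30% of diagnoses whatever the persistence. The event rate is r = 0.356 × 0.30 = 0.1068 and the competing rate is d = −ln(1 − 12-month discontinuation). Then 1 − KM = 1 − exp(−0.1068) = 10.1% at any persistence. The true value, r/(r+d) × [1 − exp(−(r+d))], is 9.1% at 20% discontinuation (d = 0.2231), 8.0% at 40% (d = 0.5108) and 6.7% at 60% (d = 0.9163). Here the difference is hidden.

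**The case against.** **Estimand.** Per-protocol follow-up concerns time on treatment. If the event is dated at diagnosis, one can ask how often patients kept on drug until a diagnosis would be diagnosed and then stop. Stopping before and after diagnosis then play different roles, and censoring the former is coherent if it is independent. Such a quantity can be imagined, but the protocol does not state it. Section 8.1 gives the purpose as burden of disease, which calls for the risk that actually occurs.

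**Stoppers can still qualify.** Discontinuation is dated 60 days after supply ends, so a patient who has in fact stopped but is diagnosed within that extension still counts. This stands as an exception. It does not help patients undiagnosed at the dated discontinuation.

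**Censoring weights.** The inverse probability of censoring weights in 8.7.2.4 are written for the gated acute MI and stroke comparisons. They would not repair this in any case, because stopping undiagnosed rules the event out.

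**Reach.** Algorithm 3 is one of five definitions and algorithm 1 matches the outcome in 8.3.2. Hypertension is descriptive only, and intention-to-treat follow-up is already planned. The Kaplan-Meier formula is spelled out for acute MI, and its use for hypertension rests on the abstract's general statement. All of this stands and keeps the point minor.

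**Stronger readings.** A reader might infer that cohorts with different persistence will show different reported risks despite equal hypertension rates. The documents do not settle this: the second model above reports equal risks, and the first magnifies a difference. A reader might also express the excess in standard errors at 20,000 users. That size does not apply, because 8.3.4 removes patients with baseline hypertension from the new-onset analysis.

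**Conclusion.** The point holds for algorithm 3 under per-protocol follow-up. The definition, the censoring rule and the estimator are all stated, and together they make the reported risk exceed the actual cumulative incidence. The direction does not depend on the rates chosen.

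The size cannot be fixed from the protocol. For assumed 12-month persistence of 70% down to 30%, the reported risk is about 1.2 to 1.8 times the true one. The excess grows as persistence falls and depends little on the hypertension rate. Contrasts of algorithm 3 between cohorts are distorted where persistence differs, in a direction that depends on how stopping relates to diagnosis.

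The severity is minor: one descriptive secondary definition under one of two follow-ups. The other four hypertension algorithms, the intention-to-treat results and the gated comparisons do not change.

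**What to change.** In 8.3.4, with a cross-reference in 8.7.2.4, choose one of two rules for algorithm 3:

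- report its cumulative incidence under intention-to-treat follow-up only; or
- in the per-protocol analysis, treat discontinuation or switching without a prior qualifying diagnosis as a competing event, estimate with Aalen-Johansen, and censor only at disenrollment or end of data.

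Under either rule, state whether the event is dated at diagnosis or at discontinuation. Leave algorithms 1, 2, 4 and 5 as they are.

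The cost is a sentence or two and a standard estimator for one definition. The algorithm 3 risk will be lower than the per-protocol figure now planned, and it will reflect persistence as well as hypertension. It should therefore be shown beside the cumulative incidence of discontinuation and the algorithm 1 result for each cohort.

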#### 6.3 Feasibility Considerations

In a recent internal Amgen study of the MarketScan® Early View database (Amgen Study 20200218), a total of 15212 erenumab-aooe users, 17239 users of other mAbs targeting the CGRP pathway, and 9242 users of onabotulinumtoxinA were identified from May 2018 through January 2020. In the same study, the rate of hypertension in new users of erenumab-aooe was 3.56 (95% confidence interval [CI]: 3.39, 3.73) per 10 PYs. In a separate study evaluating the rate of 19 vascular events in migraine patients, the rate of acute MI was 1.83 (95% CI: 1.78, 1.89) per 1000 PYs, the rate of ischemic stroke was 5.13 (95% CI: 5.04, 5.23) per 1000 PYs, and the rate of hemorrhagic stroke was 1.00 (95% CI: 0.95, 1.04) per 1000 PYs (Gill et al, 2020).

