#### Table 1. Baseline Covariates

Footnotes defined on last page of table

Page 3 of 5

Variable	Measurement	
Acute Migraine Medications (continued)		
NSAIDS	0/1 indicator at study entry for Aspirin, Celecoxib, Diclofenac, Diflunisal, Etodolac, Fenoprofen, Flurbiprofen, Ibuprofen, Indomethacin, Ketoprofen, Ketorolac, Magnesium salicylate, Meclofenamic Acid, Mefanamic Acid, Meloxicam, Nabumetone, Naproxen, Oxaprozin, Piroxicam, Rofecoxib, Salsalate, Sulindac, Tolmetin, Valdecoxib	
Opioids	0/1 indicator at study entry for Codeine, Fentanyl, Hydrocodone, Hydromorphone, Morphine Sulfate, Oxycodone, Oxymorphone, Tramadol, Alfentanil, Buprenorphine, Butorphanol tartrate, Dezocine, Dihydrocodeine, Levomethadyl, Levorphanol, Meperidine, Methadone, Nalbuphine, Opium / belladonna alkaloids / opium alkaloids, Pentazocine, Propoxyphene, Remifentanil, Sufentanil, Tapentadol	
NonNSAID NonOpioid Analgesics	0/1 indicator at study entry for Acetaminophen, Baclofen, Butalbital, Ziconotide	
Other acute migraine treatment	0/1 indicator at study entry for Lasmiditan	
Other Medications		
Contraceptives	0/1 indicator at study entry	
Anti-hypertensives		
Aldosterone antagonist	0/1 indicator at study entry	
Angiotensin receptor blockers	0/1 indicator at study entry	
Angiotensin-converting enzyme (ACE) inhibitors	0/1 indicator at study entry	
Beta-blockers	0/1 indicator at study entry	
Calcium-channel blockers	0/1 indicator at study entry	
Diuretics	0/1 indicator at study entry	
Other anti-hypertensives	0/1 indicator at study entry	
Anti-coagulants	0/1 indicator at study entry	
Anti-platelets	0/1 indicator at study entry	
Lipid-lowering agents		
Statins	0/1 indicator at study entry	
Non-statins	0/1 indicator at study entry	

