# 8.7.3 Analysis of Safety Endpoint(s)/Outcome(s)

This study will estimate the risk of hypertension, stroke, and acute MI among individuals who are exposed to erenumab-aooe, other mAbs targeting the CGRP pathway (galcanezumab-gnlm, fremanezumab-vfrm, eptinezumab-jjmr), select SOC migraine preventive medications (anti-epileptics) (topiramate, valproic acid, divalproex sodium), and onabotulinumtoxinA. Hypertension, stroke and acute MI outcomes will be identified with ICD-10-CM codes.

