116.1	ICD-10-CM Diagnosis	Hypertensive emergency	1 IP / 1 ER / 1 OP
I16.9	ICD-10-CM Diagnosis	Hypertensive crisis, unspecified	1 IP / 1 ER / 1 OP

a The outcome of hypertension will also be evaluated by restricting to the following five diagnosis codes: 110, 116, 116.0, 116.1, 116.9.

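### New onset hypertension is screened at baseline apparently by diagnosis code alone, so patients already filling antihypertensives but uncoded that year can be counted as new cases

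*Protocol*

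**What the plan says.** Section 8.3.4 states that "New onset hypertension will be the primary hypertension outcome of interest", with cumulative incidence read at 1, 2, 3, 6 and 12 months. The first case algorithm is "1 IP / 1 ER / 1 OP diagnosis (any position) of hypertension" during follow-up. The second adds an antihypertensive fill within 30 days after the code and does not ask that the drug be new. The only restriction on the at-risk set is: "When evaluating new onset hypertension, individuals with a prior history of hypertension during the baseline period will be excluded". Section 8.2.4 sets the baseline at 365 days up to and including the index date.

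The exclusion sentence does not define prior history. Several other places show how hypertension is identified:

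- Section 8.7.3: "Hypertension, stroke and acute MI outcomes will be identified with ICD-10-CM codes".
- Appendix C: the hypertension list holds diagnosis codes only, and its footnote narrows it to a smaller set of diagnosis codes ("The outcome of hypertension will also be evaluated by restricting to the following five diagnosis codes").
- Table 1 and Appendix D: hypertension appears as a comorbidity, and antihypertensive drugs (for example "Angiotensin-converting enzyme (ACE) inhibitors") appear as separate indicators.
- Section 8.3.4, exacerbation analysis: "For individuals with baseline hypertension and anti-hypertension medication use, we will also evaluate changes in medication dosage". Disease and drug use are named as two conditions.
- Section 8.7.2.2: a missing claim is read as absence of the disease.

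**The concern.** A claim for an antihypertensive is evidence of possible existing disease, and the at-risk rule does not use it. Section 8.4 says outpatient records carry at most four diagnoses, so a stable, treated condition can pass a year without being coded. Such a patient enters the new onset analysis as disease-free. The next incidental code then makes a case under algorithm 1, and a routine refill within 30 days confirms it under algorithm 2. The same patient fails the baseline-hypertension condition of the exacerbation analysis, so is misplaced in both.

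Section 6.2 notes that new onset hypertension and exacerbation of existing hypertension were both added to the product labelling. The new onset estimate therefore needs to separate the two. Nothing later in the plan corrects it. The Abstract (Data Analysis) describes the hypertension cumulative incidence as unadjusted, and the treatment weights built from the Appendix D covariates belong to the gated acute MI and stroke analyses.

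**Working it through.** **Reproducing the plan's precision figures.** Table 2 half-width = 1.96 × √(p(1−p)/N), with N = 20 000 erenumab-aooe users:

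- p = 5%: 0.302 points (Table 2: 0.30)
- p = 20%: 0.554 points (Table 2: 0.55)
- p = 30%: 0.635 points (Table 2: 0.64)

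The table reproduces. Section 8.5 expects hypertension to be common, so the 20% and 30% rows matter as much as the 5% row.

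**Model for the bias.** Let r be the true 12-month risk, f the share of the at-risk set that already has hypertension but no baseline code, and q the chance that such a patient is coded within 12 months.

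- Observed risk = (1−f)·r + f·q
- Excess = f·(q−r)

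**Inputs.** The protocol gives none of f, q or r. All are assumptions:

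- Hypertension prevalence 20-30%, with 8-15% of hypertensives uncoded in the baseline year.
- f = prevalence × uncoded / [(1−prevalence) + prevalence × uncoded].
- Low: 0.20×0.08 / (0.80+0.016) = 0.016/0.816 = 1.96%.
- High: 0.30×0.15 / (0.70+0.045) = 0.045/0.745 = 6.04%.
- q = 50% (low) to 70% (high).

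**Results.**

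| True risk r | Low: 1.96% × (50% − r) | High: 6.04% × (70% − r) | Table 2 half-width |
|---|---|---|---|
| 5% | 0.88 points | 3.93 points | 0.30 |
| 20% | 0.59 points | 3.02 points | 0.55 |
| 30% | 0.39 points | 2.42 points | 0.64 |

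At r = 5% the excess is above the half-width across the whole range. At r = 20% the low end roughly equals it. At r = 30% the low end lies inside it.

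**Check on N.** Table 2 uses the full cohort, but the new onset analysis drops coded hypertensives. Under the same assumptions the at-risk N is 20 000 × 0.816 = 16 320 (low) to 20 000 × 0.745 = 14 900 (high). The half-width becomes 0.33-0.35 points at 5% and 0.70-0.74 at 30%. The pattern does not change.

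**What the figures cover.** f counts every uncoded hypertensive, treated or not. A fill-based rule removes only those with a qualifying baseline fill, a share the protocol does not let anyone compute. The table is therefore an upper limit, under these assumptions, on what the fix can remove.

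**The case against.** The strongest reply is that the exclusion sentence never says by code only, and operational definitions of baseline covariates may sit in a statistical analysis plan that was not at hand. That stands as a caution: code-only is an inference from how the protocol treats hypertension elsewhere. It does not dispose of the point, because no part of the protocol brings drug fills into the at-risk rule and two programmers could build different at-risk sets from the sentence.

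Second, a baseline fill does not prove hypertension. Table 1 lists beta blockers, verapamil, candesartan, clonidine and lisinopril as migraine preventives. Excluding all users would remove migraine patients without hypertension. This stands, and it is why the restriction must be partial and may run beside the present definition.

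Third, there is some mitigation. Algorithms 4 (hypertensive crisis) and 5 (primary-position inpatient or emergency diagnosis) are less exposed to incidental recoding. Section 8.9.3 discusses the difficulty of claims-based hypertension, and Section 8.7.2.1 says the software can stratify risk by medication use. None of these changes the main estimate. Section 8.9.3 does not mention previously treated disease, and no such stratification is planned for this outcome.

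A reader might take the feasibility figure in Section 6.3 ("the rate of hypertension in new users of erenumab-aooe was 3.56 (95% confidence interval [CI]: 3.39, 3.73) per 10 PYs") as proof of contamination, since 1 − exp(−0.356) is about 30% in one year. The protocol does not support that. Section 6.3 does not call the rate new onset, and the eligibility criteria listed for that study in Section 8.5 include no hypertension exclusion.

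A reader might also infer that the bias differs between cohorts or falls mostly on months 1 to 3. The protocol gives no coding frequencies by cohort or over time. Under a constant recoding rate the absolute excess would be smallest early.

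**Conclusion.** The point holds as a bias in a descriptive estimate. As most naturally read, the new onset rule leaves treated but uncoded patients at risk and lets one code, or under algorithm 2 a code plus a routine refill, count them as new. The direction is upward as long as these patients are more likely to be coded than the truly disease-free (q > r). The amount is not derivable from the protocol. On the assumed f of 2-6% and q of 50-70% it is about 0.9-3.9 points at a true 12-month risk of 5% and 0.4-2.4 points at 30%, for treated and untreated uncoded patients together. That is often, but not always, larger than the sampling error the plan presents. No planned formal comparison is touched, because the gated analyses cover only acute MI and stroke. The change is worth making because this is the main result for a labelled risk and the needed variables are already collected.

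**What to change.** In Section 8.3.4:

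1. Define prior history of hypertension explicitly, naming the code list, setting and position used in the baseline period.
2. Estimate new onset hypertension also in patients with no baseline hypertension code and no baseline fill of an antihypertensive, except agents that Table 1 lists as migraine preventives. Report this beside the code-only estimate. Either may be primary and the other the sensitivity analysis, provided the choice is fixed in advance.
3. In algorithm 2, require an antihypertensive that is newly started after the code, not any fill.

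The cost is programming on drug classes already in Table 1, plus a modest loss of patients, some of whom take these drugs for other reasons. The remedy is partial: users of the exempted agents, such as lisinopril, stay at risk, and untreated uncoded hypertension is not reached at all. The report should say so.
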